5.6.2. Adverse Events

The verbatim terms used in the CRF by investigators to identify adverse events will be coded using the Medical Dictionary for Regulatory Activities (MedDRA). Any AE occurring at or after the initial administration of study intervention is considered to be treatment emergent. If the event occurs on the day of the initial administration of study intervention, and either event time or time of administration are missing, then the event will be assumed to be treatment emergent. If the event date is recorded as partial or completely missing, then the event will be considered to be treatment emergent unless it is known to be prior to the first administration of study intervention based on partial onset date or resolution date. All reported treatment-emergent adverse events will be included in the analysis. For each adverse event, the number and percentage of participants who experience at least 1 occurrence of the given event will be summarized.

Summary tables will be provided for treatment-emergent adverse events:

- AEs
- Serious AEs (SAEs)

- AEs leading to discontinuation of each study agent within a study intervention including NA
- AEs by NCI-CTAE toxicity grade
- AEs by relationship to each study agent within a study intervention including NA

In addition to the summary tables, listings will be provided for participants who:

- Had SAEs
- Had AEs leading to discontinuation of each study agent within a study intervention including NA

Incidence of other treatment-emergent adverse events of special interest listed in [Appendix 8](#) will be summarized.

A listing of participants who died will be provided.

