As of Protocol Amendment 5: The term “study intervention” throughout the protocol, refers to JNJ-3989, NA, and optional PegIFN  $\alpha$ 2a.

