**Definitions of Terms**

Study intervention	Prior to Protocol Amendment 5: JNJ-73763989 (JNJ-3989), JNJ-56136379 (JNJ-6379) and NA (either ETV, tenofovir disoproxil, or TAF) As of Protocol Amendment 5: JNJ-73763989 (JNJ-3989) and NA (either ETV, tenofovir disoproxil, or TAF)
Functional cure	HBsAg seroclearance 24 weeks after end of treatment
HBsAg or HBeAg seroclearance	HBsAg or HBeAg negativity, respectively, based on the assay used
HBsAg or HBeAg seroconversion	HBsAg or HBeAg negativity and anti-HBs or anti-HBe antibody positivity, respectively
Virologic breakthrough	Confirmed on-treatment HBV DNA increase by $>1 \log_{10}$ IU/mL from nadir or confirmed on-treatment HBV DNA level $>200$ IU/mL in participants who had HBV DNA level $<\text{LLOQ}$ of the HBV DNA assay
ALT/AST nadir	Lowest ALT/AST value during study participation

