In addition, participants who provide separate consent may receive optional treatment with PegIFN- α 2a starting after the Week 40 biopsy (or after the optional leukapheresis if applicable) but before the Week 48 visit. The duration (either 12 or 24 weeks) will be at the investigator's

discretion. This will allow investigation of whether addition of PegIFN- α 2a for 12 or 24 weeks may increase the participant's chance to achieve HBsAg loss.

All participants will complete treatment with JNJ-3989 after a fixed duration of 48 weeks. Treatment with NA will also be completed at Week 48 except for participants not meeting the NA treatment completion criteria (outlined in Protocol Section 6.6.1). In participants not meeting these criteria, NA treatment will continue during the follow-up phase. Participants who are receiving optional treatment with PegIFN- α 2a and who have not met NA treatment completion criteria at Week 48 may have NA treatment completion criteria assessed at the end of treatment with PegIFN- α 2a and stop NA if criteria are met.

[figure not shown]
In case of premature discontinuation of study agent JNJ-3989 (before Week 48), follow-up assessments should be obtained until 48 weeks after End Of Study Intervention (EOSI) unless the participant withdraws consent. Participants who withdraw consent will be offered an optional safety follow-up visit.

The SAP will use throughout the document the following definitions:

- *Study treatment* refers to JNJ-6379, JNJ-3989, NA (either ETV, TD, or TAF), and PegIFN- α 2a.
- *Study agent* refers to JNJ-6379 and JNJ-3989
 - *Arm* refers to:
 - Arm 1: JNJ-3989+JNJ-6379+NA
 - Arm 2: JNJ-3989+NA

A schematic overview of the study is presented in [Figure 1](#) (Prior to Protocol Amendment 5) and in [Figure 2](#) (As of Protocol Amendment 5).

[figure not shown]
Figure 1: Schematic Overview of the Study – Prior to Protocol Amendment 5

ETV: entecavir; N: number of participants; LB: (planned) liver biopsy; NA: nucleos(t)ide analog; Q4W: once every 4 weeks; qd: once daily; TAF: tenofovir alafenamide; TD: tenofovir disoproxil; QW: once weekly

* Participants who provide separate consent may receive optional treatment with PegIFN- α 2a starting after the Week 40 biopsy (or after the optional leukapheresis visit if applicable) for a duration of either 12 or 24 weeks at the investigator's discretion.

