5. STATISTICAL ANALYSES

5.1. General Considerations

5.1.1. Analysis Phase

The analysis phases are defined in [Table 1](#) below. Note that the screening, open-label, and follow-up phases are non-overlapping and cover the entire study period. The optional PegIFN- α 2a treatment phase, in contrast, may overlap with both the open-label and follow-up phases.

Table 1: Analysis Phases Start and End Dates

Analysis phase	Start date	End date
Screening	The date of signing the informed consent	1 day before the first study agent intake (JNJ-3989 or JNJ-6379)
Open-label study intervention	Date of first study agent intake (JNJ-3989 or JNJ-6379)	Earliest of the following dates: 
 • Early discontinuation date for JNJ-3989 + 5 days^a • Study termination date • Max{ 
 • Date of last JNJ-3989 intake, • Date of Week 48 visit • } + 5 days^a • Cut-off date^b
Follow-up	End date of open-label phase + 1 day	Min (study termination date, study completion date, cut-off date ^b)
Optional PegIFN- α 2a treatment	Date of first PegIFN- α 2a intake	Min (Date of last PegIFN- α 2a intake + 5 days ^a , cut-off date ^b)

a : Addition of 5 days is only applicable for Adverse Events and Concomitant Medications.

b : Cut-off dates will be defined to match the prespecified timepoints for interim analyses, the primary analysis and the final analysis, respectively.

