5.1.3. On-Treatment and Off-Treatment Period

The on-treatment period begins with the first drug intake and finishes with the maximum between:

- Last dose of NA + 2 days
- Last dose of PegIFN- α 2a +10 days
- Last dose of JNJ-3989 + 28 days

The off-treatment period starts after the end of on-treatment period and stops if the NA re-treatment starts.

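### The SAP's AE-by-relationship and AE-discontinuation outputs leave out PegIFN-α2a by the SAP's own definitions; secondarily, some AE phase ends do not match its own exposure and on-treatment windows

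*SAP*

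**What the plan says.** SAP 1.2 sets defined terms for the whole document. *Study agent* "refers to JNJ-6379 and JNJ-3989". *Study treatment* is the wider term: it "refers to JNJ-6379, JNJ-3989, NA (either ETV, TD, or TAF") and, at the end of the list, PegIFN-α2a.

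SAP 5.6.2 uses the narrower term. It plans a table of "AEs by relationship to each study agent within a study intervention including NA" and another of "AEs leading to discontinuation of each study agent within a study intervention including NA", and repeats the second item as a participant listing. NA, which is not a study agent, is added by name. PegIFN is not.

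The protocol treats PegIFN as part of the regimen. Its intervention table (Section 6.1 and synopsis) classes PegIFN as investigational, and the synopsis says that, as of Amendment 5, the term study intervention "refers to JNJ-3989, NA, and optional PegIFN". Protocol Appendix 1 differs: "As of Protocol Amendment 5: JNJ-73763989 (JNJ-3989) and NA (either ETV, tenofovir disoproxil, or TAF"), with no PegIFN.

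On timing, SAP Table 1 (5.1.1) ends the open-label phase at the earliest of several dates. One is "Early discontinuation date for JNJ-3989 + 5 days". Another is the later of the last JNJ-3989 intake and the Week 48 visit, plus 5 days. The PegIFN phase ends 5 days after the last intake. The 5 days apply only to AEs and concomitant medications. SAP 5.1.3 ends the on-treatment period at the latest of three dates: NA plus 2 days, PegIFN plus 10 days, and "Last dose of JNJ-3989 + 28 days". SAP 5.6.1 counts PegIFN exposure to the last dose plus 6 days.

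**The concern.** PegIFN has a well-established and broad toxicity profile. Protocol 2.3.2.1 lists neuropsychiatric, autoimmune, ischemic, ophthalmologic, hematological and infectious disorders. Finding out whether adding PegIFN improves response is a stated aim (Protocol 2.1 and 4.1), and weighing that benefit needs the related AEs and the AEs that ended treatment.

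Timing makes the omission matter. With a start at nominal Week 40 and the last JNJ-3989 injection at Week 44, 8 of 12 or 20 of 24 PegIFN weeks fall after that injection. Protocol 7.1 also says that JNJ-3989 continues if PegIFN is stopped. An AE that stops PegIFN alone therefore produces no JNJ-3989 or NA discontinuation through which it could enter these outputs.

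The phase ends raise a smaller question. Safety is summarised by analysis phase, so an AE soon after the last injection can be reported under follow-up while other SAP rules still count that time as exposed or on treatment.

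**Working it through.** **1. Coverage of the three outputs.** Here the check is a comparison of definitions.

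| Treatment | Study agent (SAP 1.2) | Added by name in 5.6.2 | In the three outputs as written |
|---|---|---|---|
| JNJ-3989 | yes | not needed | yes |
| JNJ-6379 | yes | not needed | yes |
| NA | no | yes | yes |
| PegIFN-α2a | no | no | **no** |

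What else in the SAP covers PegIFN safety:
- Overall AE and SAE tables, with the SAE and death listings, include events during PegIFN, but the plan does not split them by relationship to it.
- PegIFN has its own analysis phase (Table 1) and is a Yes/No safety subgroup (Table 6). Both describe AEs in exposed participants, not AEs attributed to PegIFN.
- SAP 5.2 summarises and lists reasons for stopping study treatment, which includes PegIFN. It does not call for the AE terms.
- Table 7 has a general row for AEs causing treatment discontinuation, not specified by drug.
- The special-interest terms in Appendix 8 cover ALT/AST, renal, hematologic and cholesterol events. They do not cover psychiatric, thyroid or eye events.

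**2. PegIFN phase end.** Days after the last dose: 5 (Table 1), 6 (5.6.1), 10 (5.1.3). Shortfall: 6 − 5 = 1 day against exposure; 10 − 5 = 5 days against the on-treatment rule.

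**3. JNJ-3989, completers.** Target days from SAP Table 2 are 309 (Week 44) and 337 (Week 48).
- Phase end = max(309, 337) + 5 = 342.
- Coverage after the last injection = 342 − 309 = 33 days.
- With the ±3-day visit windows: (334 + 5) − 312 = 27 to (340 + 5) − 306 = 39 days.
- Edge case: Protocol 6.4 allows a missed injection up to 3 weeks late. A Week 44 injection on day 330 gives 342 − 330 = 12 days.

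**4. JNJ-3989, early discontinuers.** Let L be the days from last injection to recorded discontinuation. Coverage = L + 5; shortfall against 28 days = max(0, 23 − L). The documents do not give L, so the values below are assumptions.

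| L (days) | 0 | 7 | 14 | 21 | 28 |
|---|---|---|---|---|---|
| Coverage | 5 | 12 | 19 | 26 | 33 |
| Shortfall | 23 | 16 | 9 | 2 | 0 |

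**5. What happens to an AE after the phase closes.** Under SAP 5.6.2 any AE from first dose onward is treatment-emergent, with no end date, and all such AEs are analysed. Follow-up begins the day after the open-label phase ends. Causality is the investigator's judgement (Protocol Appendix 4). A later AE changes phase; it keeps its emergent status and its causality assessment.

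**The case against.** The best defence is that the wording is loose, not exclusionary. The phrase in 5.6.2 already departs from the definition by adding NA. SAP 5.6.1 counts PegIFN among the agents, and the change-log entry for 5.1.3 speaks of the last study agent for a rule that covers NA and PegIFN. The SAP is to be read with the protocol, whose synopsis includes PegIFN in the study intervention. This stands as far as intent goes: nothing shows a decision to exclude PegIFN. It does not settle what a programmer should produce, because SAP 1.2 applies its definitions throughout and only NA was added.

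On the phase ends, it is fair to say that 28 days is one component of a maximum in 5.1.3, that participants who stay on NA remain on treatment longer under that rule, and that 5.6.2 does not refer to 5.1.3. The two constructs can coexist, so this is a matter of consistency.

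A reader might infer more than the documents support:
- *That JNJ-3989 toxicity goes unattributed.* JNJ-3989 is in all three outputs, and causality does not depend on a date window.
- *That late AEs are lost.* The screening, open-label and follow-up phases together cover the whole study.
- *That the AE phase always closes 5 days after a 4-weekly injection.* On-schedule completers have about 33 days.
- *That all 13 PegIFN-specific stopping reasons in Protocol 7.1 would escape the discontinuation outputs.* Hepatic decompensation, serious hypersensitivity, and low platelets or neutrophils can also lead to stopping JNJ-3989, and would then be captured while it is ongoing.

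**Conclusion.** The main point holds. Read with its own definitions, the SAP provides no AE-by-relationship or AE-discontinuation output for PegIFN, and the other planned summaries compensate only in part. The gap is confined to PegIFN and to three outputs. It is a specification defect that should be corrected, not a threat to the primary endpoint.

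The secondary point holds as phase labelling only: 5 days for PegIFN against the 10-day window, and 0 to 23 days for early JNJ-3989 discontinuers. The 23 days is a worst case in which discontinuation is recorded on the day of the last injection. That no AE drops out rests on the SAP's open-ended definition; Protocol 9.4.2 ties intervention-emergent AEs largely to onset in the intervention phase, so the SAP definition should be confirmed as the one in force.

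The missing PegIFN entry in Protocol Appendix 1 conflicts with the synopsis but is editorial.

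**What to change.** In the three SAP 5.6.2 outputs (relationship table, discontinuation table, discontinuation listing), replace the study-agent wording with *each study treatment (JNJ-3989, JNJ-6379, NA, PegIFN-α2a)*. The documents do not show whether the CRF records relationship to PegIFN separately; confirm this, because the relationship column depends on it. Add PegIFN to the study-intervention entry in Protocol Appendix 1.

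In SAP Table 1, end the PegIFN phase for AEs at last dose + 10 days. For early JNJ-3989 discontinuers, end the open-label AE phase at the later of discontinuation date + 5 days and last injection + 28 days. The later-of form matters: last injection + 28 days alone would shorten the phase whenever discontinuation is recorded more than 23 days after the last injection (from 33 to 28 days when L = 28). The same form would also cover a completer with a late Week 44 injection.

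The cost is SAP wording, a few extra table columns, and a slight shift of AEs from follow-up to the open-label or PegIFN phase. If the CRF already holds the PegIFN relationship, no new data are needed.

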5.6.3. Additional Safety Assessments

5.6.3.1. Clinical Laboratory Tests

Laboratory data will be summarized by category of laboratory test. The different categories and laboratory tests used in the analysis are listed in [Table 5](#).

Table 5: Laboratory Parameters

Laboratory Category	Parameters		
Hematology	Platelet count RBC count Hemoglobin Hematocrit Reticulocyte count Reticulocyte index	RBC Indices: Mean corpuscular volume Mean corpuscular hemoglobin Mean corpuscular hemoglobin concentration	WBC count with Differential: Neutrophils Lymphocytes Monocytes Eosinophils Basophils
Blood Coagulation	Activated partial thromboplastin time International normalized ratio Prothrombin time		
Clinical Chemistry	Sodium Potassium Chloride Bicarbonate Blood urea nitrogen Creatinine Cystatin C (for Panel 3 only) Glucose AST/Serum glutamic-oxaloacetic ALT/Serum glutamic-oxaloacetic Gamma-glutamyltransferase (GGT) Total, conjugated and unconjugated bilirubin Alkaline phosphatase Creatine phosphokinase		
	Lactic acid dehydrogenase Uric acid Calcium Phosphate Albumin Total protein Total cholesterol High-density lipoprotein cholesterol Low-density lipoprotein cholesterol Triglycerides Magnesium Lipase Amylase		
	Note: Creatinine clearance (eGFR calculated by the CKD-EPI formula, denoted as eGFRcr) will be assessed for Panels 1 and 2. For Panel 3, eGFR will be calculated based		

	on cystatin C in serum (calculated by the CKD-EPI cystatin C equation, denoted as eGFRcys)	
Routine Urinalysis	Dipstick Specific gravity pH Glucose Protein Blood Ketones Bilirubin Urobilinogen Nitrite Leukocyte esterase	Sediment (if dipstick result is abnormal) RBCs WBCs Epithelial cells Crystals Casts Bacteria
Urine Chemistry (quantitative measurement)	Creatinine Sodium Phosphate	Glucose Protein Albumin
Renal Biomarkers	Retinol binding protein Beta-2-microglobulin	

Clinical laboratory tests will be displayed for the participants included in the safety analysis set by study panel and study phase.

Descriptive statistics and graphical displays will be presented for all chemistry, hematology, and urinalysis laboratory tests at scheduled time points.

Change from baseline over time will be summarized for chemistry, hematology, urinalysis tests and renal biomarkers and displayed.

Abnormality criteria ([based on the criteria specified in the DAIDS Toxicity Grading Scale (see Clinical Protocol Appendix 8, DAIDS Table)]) will be applied to baseline and postbaseline values or in accordance with the normal ranges of the clinical laboratory if no gradings are available.

Postbaseline abnormalities will be compared with their corresponding baseline result:

- For toxicity grades, treatment emergent (TE) will be concluded if the postbaseline grade is worse than the baseline grade.
- For abnormalities based on normal range and/or criteria: If the postbaseline value is above the upper limit and the baseline value is below the upper limit (e.g., Normal or Low), then the postbaseline abnormality will be considered TE. The same applies to the postbaseline value being below the lower limit with the baseline value being above the lower limit (e.g., Normal or High).
- If the baseline value is missing, a postbaseline abnormality will always be considered as TE.

For each lab parameter, a worst-case analysis will be performed by using the worst abnormality and/or worst toxicity grade lab value and time point per participant ([Appendix 9](#)). The worst toxicity case is the value associated to the highest toxicity grade and is derived per parameter and

toxicity direction (hypo / hyper). Worst-case will be derived within each phase, including unscheduled assessments. For abnormalities, in case the same subject has both abnormalities (low and high) for the same lab test within the same phase, the participant will be counted in the analysis for both toxicity directions (abnormally high and low).

Imputation rules:

In case continuous laboratory results are not numerically expressed, but as a character (e.g., 'less than 2', '>25'), these results will be numerically imputed as follows:

- If the analysis result contains '<' then the result will be multiplied by 0.999 (e.g., <6.1 becomes 6.0939).
- If analysis result contains '>' then the result will be multiplied by 1.001 (e.g., >6.1 becomes 6.1061).
- If analysis result contains ' \leq ' or ' \geq ' then only the numeric portion of the result will be used.

This also applies to normal limits expressed as such.

Shift tables will be provided summarizing the shift in laboratory values from baseline over time with respect to abnormality criteria (low, normal, high) for each laboratory parameter by study phase.

The cross-tabulations of the worst toxicity grades over time versus baseline grade and the worst abnormalities versus baseline grade per parameter and per analysis phase will be presented including also the number of participants per worst grade and the number of participants per abnormality.

A tabulation of percentage and number of the participants who have treatment-emergent worst toxicity grades and treatment-emergent worst abnormalities per parameter and analysis phase will be included. The incidence table of worst toxicity grade abnormality in laboratory parameters will be also presented stratified by the subgroup of interests identified in Section [5.7.4](#).

Plots of mean (+/- SE) values and changes from baseline over time for alanine transferase (ALT), aspartate aminotransferase (AST), alkaline phosphatase, hemoglobin, neutrophils, platelets, bilirubin (direct and indirect), lipase, amylase/pancreatic amylase, activated partial thromboplastin time, prothrombin time and phosphate will be presented by study panel. Spaghetti-plots for selected laboratory parameters will be presented by study panel over time (with Week shown on x-axis).

A listing including all parameters with at least one treatment-emergent toxicity or abnormality per participant (exclusion of urinalysis) will be generated.

5.6.3.1.1. Creatinine and Glomerular Filtration

Creatinine and glomerular filtration analyses will be analysed over time.

5.6.3.1.1.1. eGFR

Stages of eGFR (eGFRcr or eGFRcys, as described in [Table 5](#)) at baseline versus the minimum corresponding post-baseline eGFR value and the last available value will be summarized by count and percent of participants. Stage of chronic kidney disease (CKD) are defined as follows: 1 (Normal): eGFR ≥ 90 ; 2 (Mild): eGFR 60-89; 3 (Moderate): eGFR 30-59; 4 (Severe): eGFR <30 .

In addition to the above, the number and proportion of participants with a $<10\%$, $10-30\%$, $30-50\%$ and $\geq 50\%$ decrease from baseline will be tabulated.

Scatter plots of eGFR (eGFRcr or eGFRcys) versus other renal biomarkers (total urine protein, total urine albumin, urine protein to creatinine ratio [UPCR], urine albumin to creatinine ratio [UACR], retinol binding protein (RBP) and beta-2-microglobulin, RBP to creatinine ratio and beta-2-microglobulin to creatinine ratio, and urine fractional excretion of phosphate [FEPO4]) will also be presented.

5.6.3.1.1.2. Proximal Renal Tubular Function

Proteinuria by Quantitative Assessment

Total urine protein, total urine albumin, UPCR and UACR will be summarized by study panel and visit using descriptive statistics.

The number and proportion of participants with UACR and UPCR results in the following categories over time will be tabulated:

- UACR: < 30 , ≥ 30 to 300 , >300 mg/g
- UPCR: < 200 mg/g versus ≥ 200 mg/g

Median (Q1, Q3) percent change from baseline over time will be plotted by study panel.

The evolution over time of total urine protein and total urine albumin will also be presented.

Proteinuria by Urinalysis (Dipstick)

Treatment-emergent proteinuria by urinalysis (dipstick) over time will be summarized by study panel. Cross-tabulation of grades overtime versus baseline will also be presented.

Other Renal Biomarkers

Selected renal biomarkers RBP and beta-2-microglobulin, RBP to creatinine ratio and beta-2-microglobulin to creatinine ratio will be summarized by study panel and visit using descriptive statistics.

The proportions of participants with beta-2-microglobulin to creatinine ratio ≤ 343.5 $\mu\text{g/g}$ and >343.5 $\mu\text{g/g}$ will be tabulated.

The number and proportion of participants with RBP to creatinine ratio results in the following categories overtime will be tabulated:

- < 50 years of age: < 130 mcg/g creatinine, \geq 130 mcg/g creatinine
- \geq 50 years of age: < 172 mcg/g creatinine, \geq 172 mcg/g creatinine

Phosphate excretion

Other renal biomarkers include FEPO4 that will be summarized by study panel and visit using descriptive statistics.

FEPO4 will be calculated as follows:

- Based on unadjusted serum creatinine:

$$\text{FEPO4 (\%)} = (\text{SCr} \times \text{UPO4}) / (\text{SPO4} \times \text{UCr}) \times 100 (\%)$$

Where SCr is serum creatinine concentration, UPO4 is urine phosphate concentration, SPO4 is serum phosphate concentration, and UCr is urine creatinine concentration.

The proportions of participants with FEPO4 \leq 10% and $>$ 10% will be tabulated.

The baseline, post-baseline, and change from baseline in FEPO4 will be summarized by study panel and visit using descriptive statistics. Median (Q1, Q3) change from baseline in FEPO4 over time will be plotted by study panel.

Subclinical renal proximal tubulopathy

Potential Markers of Renal Proximal Tubulopathy are:

1. Confirmed increase in serum creatinine \geq 0.40 mg/dL from baseline.
2. Confirmed \geq 2 grade level increase from baseline in graded proteinuria
3. Confirmed \geq 1 grade level increase from baseline in graded hypophosphatemia
4. Confirmed \geq 1 grade level increase from baseline in graded glycosuria concurrent with serum glucose \leq 100 mg/dL (normoglycemic glycosuria)

A confirmed laboratory abnormality is defined as an abnormality observed at 2 consecutive post-baseline measurements or an abnormality observed at 1 measurement followed by study drug discontinuation

A subclinical renal proximal tubulopathy will be defined as confirmed abnormalities in any 2 out of the 4 renal parameters (serum creatinine and one or more of the 3 other markers of tubular dysfunction).

Baseline Subclinical renal proximal tubulopathy

Potential Markers of Renal Proximal Tubulopathy at Baseline

1. Grade ≥ 1 serum creatinine
2. Grade ≥ 2 proteinuria
3. Grade ≥ 1 hypophosphatemia
4. Grade ≥ 1 glycosuria concurrent with serum glucose ≤ 100 mg/dL (normoglycemic glycosuria)

A baseline subclinical renal proximal tubulopathy will be defined as abnormalities in any 2 out of the 4 renal parameters (serum creatinine + 1 or more of the 3 other markers of tubular dysfunction).

